12.0 MEASUREMENT OF EFFECT

12.1 CRITERIA FOR EVALUATION OF THERAPY EFFECTIVENESS

Tumor response and regrowth can frequently be difficult to measure directly. Three CT scans performed will be dual energy at the following time points: Baseline, Day 14 and Cycle 3. Serial CT scans will be performed at all additional time points based on tumor types may provide a guide to the actual course. Time interval to progression will be measured from registration until deterioration is documented by the individual investigator using these guides.

- **Progression-free survival** will be measured from the start of cancer treatment until the first occurrence of progression or death.
- **Overall survival** will be measured from the start of cancer treatment until death.
The quality of survival will be measured by functional classification and performance status

Patients will be followed both clinically and radiographically for evidence of tumor progression. Post-treatment scans will be compared to the baseline CT scan and responses will be assessed using response evaluation criteria in solid tumors (RECIST 1.1).

12.2 RESPONSE CRITERIA

For the purposes of this study, patients should be re-evaluated for response every 8 weeks (every other cycle) by CT scans for body images.

12.2.1 Response and progression will be evaluated in this study using the new international criteria proposed by the revised Response Evaluation Criteria in Solid Tumors (RECIST) guideline (version 1.1) [Eur J Ca 45:228-247, 2009]. Changes in the largest diameter (unidimensional measurement) of the tumor lesions and the shortest diameter in the case of malignant lymph nodes are used in the criteria.

- Evaluable for toxicity: All patients will be evaluable for toxicity from the time of their first treatment with SLM. Toxicities will be measured using the CTCAE criteria, version 4.03
- Evaluable for objective response: Only those patients who have measurable disease present at baseline, have received at least one cycle of therapy, and have had their disease re-evaluated will be considered evaluable for response. These patients will have their response classified according to the definitions stated below. (Note: Patients who exhibit objective disease progression prior to the end of cycle 1 will also be considered evaluable.)
- Evaluable Non-Target Disease Response: Patients who have lesions present at baseline that are evaluable but do not meet the definitions of measurable disease, have received at least one cycle of therapy, and have had their disease re-evaluated will be considered evaluable for non-target disease. The response assessment is based on the presence, absence, or unequivocal progression of the lesions.

12.2.2 Disease Parameters

- Measurable disease: Measurable lesions are defined as those that can be accurately measured in at least one dimension (longest diameter to be recorded) as ≥ 20 mm by chest x-ray, as ≥ 10 mm with CT scan, or ≥ 10 mm with calipers by clinical exam. All tumor measurements must be recorded in millimeters (or decimal fractions of centimeters).
- Malignant lymph nodes. To be considered pathologically enlarged and measurable, a lymph node must be ≥ 15 mm in short axis when assessed by CT scan (CT scan slice thickness recommended to be

no greater than 5 mm). At baseline and in follow-up, only the short axis will be measured and followed.

- **Non-measurable disease.** All other lesions (or sites of disease), including small lesions (longest diameter <10 mm or pathological lymph nodes with ≥ 10 to <15 mm short axis), are considered non-measurable disease. Bone lesions, ascites, pleural/pericardial effusions, lymphangitis cutis/pulmonitis, inflammatory breast disease, and abdominal masses (not followed by CT or MRI), are considered as non-measurable.
- Note: Cystic lesions that meet the criteria for radiographically defined simple cysts should not be considered as malignant lesions (neither measurable nor non-measurable) since they are, by definition, simple cysts.

Cystic lesions thought to represent cystic metastases can be considered as measurable lesions, if they meet the definition of measurability described above. However, if non-cystic lesions are present in the same patient, these are preferred for selection as target lesions.

- **Target lesions.** All measurable lesions up to a maximum of 2 lesions per organ and 3 lesions in total, representative of all involved organs, should be identified as **target lesions** and recorded and measured at baseline. Target lesions should be selected on the basis of their size (lesions with the longest diameter), be representative of all involved organs, but in addition should be those that lend themselves to reproducible repeated measurements. It may be the case that, on occasion, the largest lesion does not lend itself to reproducible measurement in which circumstance the next largest lesion which can be measured reproducibly should be selected. A sum of the diameters (longest for non-nodal lesions, short axis for nodal lesions) for all target lesions will be calculated and reported as the baseline sum diameters. If lymph nodes are to be included in the sum, then only the short axis is added into the sum. The baseline sum diameters will be used as reference to further characterize any objective tumor regression in the measurable dimension of the disease.
- **Non-target lesions.** All other lesions (or sites of disease) including any measurable lesions over and above the 3 target lesions should be identified as **non-target lesions** and should also be recorded at baseline. Measurements of these lesions are not required, but the presence, absence, or in rare cases unequivocal progression of each should be noted throughout follow-up.

12.2.3 Methods for Evaluation of Measurable Disease

All measurements should be taken and recorded in metric notation using a ruler or calipers. All baseline evaluations should be performed as closely as possible to the beginning of treatment and never more than 4 weeks before the beginning of the treatment.

The same method of assessment and the same technique should be used to characterize each identified and reported lesion at baseline and during follow-up. Imaging-based evaluation is preferred to evaluation by clinical examination unless the lesion(s) being followed cannot be imaged but are assessable by clinical exam.

- **Conventional CT and/or MRI:** This guideline has defined measurability of lesions on CT scan based on the assumption that CT slice thickness is 5 mm or less. If CT scans have slice thickness greater than 5 mm, the minimum size for a measurable lesion should be twice the slice thickness.

- Dual Energy CT:
 - Contrast: 50% saline mixed with 50% 370mg/ml Iopamidol delivered at 4ml/s (4ml/s (35 s+ 5s) = 160ml of which 80ml is contrast) with delay of 35s (for chest) and 70s (for abdomen pelvis)
 - Positioning: Cranialcaudal acquisition with scan coverage (DFOV) from pubic symphysis to apex of lungs (DFOV to match prior visit). Acquisition at coached total lung capacity (TLC) (recorded for DECT)
 - Acquisition: CHEST: The spiral DECT contrast scan with dose modulation with tube A: 120 ref mAs/80kV, tube B: 67 ref mAs/Sn150 kV, with a pitch of 0.55 and rotation time of 0.25sec. The CTDIvol is assumed to be 4.28mGy, with total DLP of 143.2mGy*cm for a 30cm scan.
 - Acquisition: ABDOMEN: The spiral dual energy contrast abdomen/pelvis scan protocol uses dose modulation with tube A: 190 ref mAs/100kV, tube B: 95 ref mAs/Sn150 kV, with a pitch of 0.55 and rotation time of 0.25sec. The CTDIvol is assumed to be 10.41mGy, with total DLP of 553.7mGy*cm for a 50cm scan.
 - Reconstruction: R1: 0.75 x0.5; R2: 2.0 x 1.4, Qr40(Admire 5), FOV to match prior visits, Energy Series: A, B and M. Keep Raw data.
- Bone Scan: Will be ordered if the patient has new bone pain, or with elevated alkalinephosphatase, and in patients with known bony metastasis, looking for any new or worsening old bony lesions.
- PET-CT: At present, the low dose or attenuation correction CT portion of a combined PET-CT is not always of optimal diagnostic CT quality for use with RECIST measurements. However, if the site can document that the CT performed as part of a PET-CT is of identical diagnostic quality to a diagnostic CT (with IV and oral contrast), then the CT portion of the PET-CT can be used for RECIST measurements and can be used interchangeably with conventional CT in accurately measuring cancer lesions over time. Note, however, that the PET portion of the CT introduces additional data which may bias an investigator if it is not routinely or serially performed.

12.3 RESPONSE CRITERIA.

12.3.1.1 Evaluation of Target Lesions

- Complete Response (CR): Disappearance of all target lesions. Any pathological lymph nodes (whether target or non-target) must have reduction in short axis to <10 mm.
- Partial Response (PR): At least a 30% decrease in the sum of the diameters of target lesions, taking as reference the baseline sum diameters.
- Progressive Disease (PD): At least a 20% increase in the sum of the diameters of target lesions, taking as reference the smallest sum on study (this includes the baseline sum if that is the smallest on study). In addition to the relative increase of 20%, the sum must also demonstrate an absolute increase of at least 5 mm. (Note: the appearance of one or more new lesions is also considered progression).
- Stable Disease (SD): Neither sufficient shrinkage to qualify for PR nor sufficient increase to qualify for PD, taking as reference the smallest sum diameters while on study.

12.3.1.2 Evaluation of Non-Target Lesions

- Complete Response (CR): Disappearance of all non-target lesions and normalization of tumor marker level. All lymph nodes must be non-pathological in size (<10 mm short axis).
Note: If tumor markers are initially above the upper normal limit, they must normalize for a patient to be considered in complete clinical response.
- Non-CR/Non-PD: Persistence of one or more non-target lesion(s) and/or maintenance of tumor marker level above the normal limits.
- Progressive Disease (PD): Appearance of one or more new lesions and/or *unequivocal progression* of existing non-target lesions. *Unequivocal progression* should not normally trump target lesion status. It must be representative of overall disease status change, not a single lesion increase.

Although a clear progression of “non-target” lesions only is exceptional, the opinion of the treating physician should prevail in such circumstances, and the progression status should be confirmed at a later time by the review panel (or Principal Investigator).

12.3.1.3 Evaluation of Best Overall Response

- The best overall response is the best response recorded from the start of the treatment until disease progression/recurrence (taking as reference for progressive disease the smallest measurements recorded since the treatment started). The patient's best response assignment will depend on the achievement of both measurement and confirmation criteria (Table 4).

12.3.1.4 Duration of Response

- Duration of overall response: The duration of overall response is measured from the time measurement criteria are met for CR or PR (whichever is first recorded) until the first date that recurrent or progressive disease is objectively documented (taking as reference for progressive disease the smallest measurements recorded since the treatment started).
The duration of overall CR is measured from the time measurement criteria are first met for CR until the first date that progressive disease is objectively documented.
- Duration of stable disease: Stable disease is measured from the start of the treatment until the criteria for progression are met, taking as reference the smallest measurements recorded since the treatment started, including the baseline measurements.

12.3.1.5 Progression-Free Survival

- PFS is defined as the duration of time from start of treatment to time of progression or death, whichever occurs first.

Table 4: For Patients with Measurable Disease (i.e., Target Disease)

Target Lesions	Non-Target Lesions	New Lesions	Overall Response	Best Overall Response when Confirmation is Required*
CR	CR	No	CR	≥ 4 wks. Confirmation**
CR	Non-CR/Non-PD	No	PR	≥ 4 wks. Confirmation**
CR	Not evaluated	No	PR	
PR	Non-CR/Non-PD/not evaluated	No	PR	
SD	Non-CR/Non-PD/not evaluated	No	SD	Documented at least once ≥ 4 wks. from baseline**
PD	Any	Yes or No	PD	no prior SD, PR or CR
Any	PD***	Yes or No	PD	
Any	Any	Yes	PD	

* See RECIST 1.1 manuscript for further details on what is evidence of a new lesion.
 ** Only for non-randomized trials with response as primary endpoint.
 *** In exceptional circumstances, unequivocal progression in non-target lesions may be accepted as disease progression.
Note: Patients with a global deterioration of health status requiring discontinuation of treatment without objective evidence of disease progression at that time should be reported as "*symptomatic deterioration*." Every effort should be made to document the objective progression even after discontinuation of treatment.

For Patients with Non-Measurable Disease (i.e., Non-Target Disease)

Non-Target Lesions	New Lesions	Overall Response
CR	No	CR
Non-CR/non-PD	No	Non-CR/non-PD*

Not all evaluated	No	not evaluated
Unequivocal PD	Yes or No	PD
Any	Yes	PD
* ‘Non-CR/non-PD’ is preferred over ‘stable disease’ for non-target disease since SD is increasingly used as an endpoint for assessment of efficacy in some trials so to assign this category when no lesions can be measured is not advised		

12.3.1.6 Response Review

Patients with measurable disease will be assessed by standard criteria. The purpose of tumor measurements will be to assess benefit to the patients from treatment and to determine appropriateness for continuing on study. For the purposes of this study, patients should be re-evaluated every week to every six weeks according to the study guidelines and undergo imaging studies as highlighted in the study calendar. Following documentation of an objective response, confirmatory scans will also be obtained a minimum of eight weeks later.

13.0 DATA REPORTING / REGULATORY REQUIREMENTS

Adverse event lists, guidelines, and instructions for AE reporting can be found in Section 8 (Adverse Events: List and Reporting Requirements).

13.1 REGULATORY COMPLIANCE/GOOD CLINICAL PRACTICES

This study will be conducted in accordance with the following regulations and guidelines, to include but not limited to:

- Declaration of Helsinki (October 2000)
- Current ICH Guideline for Good Clinical Practice
- 21 CFR 50: Protection of Human Subjects
- 21 CFR 54: Financial Disclosure by Clinical Investigators
- 21 CFR 56: Institutional Review Boards
- 21 CFR 312: Investigational New Drug Application

13.2 REGULATORY DOCUMENTATION

Prior to study start-up, investigators will submit the following documents to the sponsor, as outlined in the Essential Documents Section 8.0 of the ICH Guidelines for Good Clinical Practice to include but not limited to:

- Signed Confidentiality Agreement
- Signed Clinical Trial Agreement, if applicable
- Up-to-date signed and dated Curriculum vitae and copies of medical licenses for Principal and one sub/co-investigator with CVs for all investigators to be submitted promptly
- Financial Disclosure form for Principal and one sub/co-investigator with financial disclosure forms for all investigators to be submitted promptly
- FDA Form 1572
- IRB approval to conduct the study: IRB-approved informed consent form,
- Name and address of the IRB with the statement that it is organized and operates according to GCP and the applicable laws and regulations
- IRB membership roster
- Local laboratory certifications, its name and address
- Local laboratory normal ranges (a dated copy for tests to be performed during the study).
- Financial agreement, if applicable.
- Signed and dated Investigator Agreement page of the final protocol and amendments, where applicable.

13.3 INSTITUTIONAL REVIEW BOARD (IRB)

This Trial will be undertaken only after full approval of the protocol and addenda has been obtained from a local IRB and a copy of this approval has been received by the sponsor. The IRB must be informed of all subsequent protocol amendments issued by the sponsor. Reports on and reviews of, the trial and its progress will be submitted to the IRB by the investigator at intervals set forth in its guidelines.

13.4 INFORMED CONSENT

Each subject must give written consent and sign other locally required documents after the nature of the study has been fully explained. The informed consent form must be signed prior to performance of any study-related activity with the exception of baseline imaging (if already obtained within 14 days prior to starting study treatment) and baseline lab studies (if already obtained within 7 days prior to starting study treatment). The informed consent form that is used must be approved both by the sponsor and by the reviewing IRB. The Informed Consent should be in accordance of the Declaration of Helsinki, current International Conference on Harmonization (ICH) and Good Clinical Practices (GCP) guidelines.

13.5 ADMINISTRATIVE REQUIREMENTS

13.5.1 Protocol modifications

The investigator will not modify this protocol without obtaining permission from the sponsor. All protocol amendments must be issued by the sponsor, signed and dated by the investigator, and should not be implemented without prior IRB approval, except where necessary to eliminate immediate hazards to the subjects or when the change(s) involves only logistical or administrative aspects of the trial (e.g., change in monitor(s), change of telephone number(s)).

In situations requiring a modification, the investigator or other physician in attendance will contact the medical monitor by fax or telephone. This contact must be made prior to implementing any departure from protocol. Contact with the sponsor must be made as soon as possible in order to outline an appropriate course of action.

13.5.2 Record Retention

In compliance with the ICH/GCP guidelines the investigator/institution will maintain all CRFs and all source documents that support the data collected from each patient, and all trial documents as specified in Essential Documents for the Conduct of a Clinical Trial and as specified by the applicable regulatory requirement(s).

The investigator/institution will take measures to prevent accidental or premature destruction of these documents. Essential documents must be retained until at least two years after the last approval of a marketing application in an ICH region or at least two years have elapsed since the formal discontinuation of clinical development of the investigational product.

These documents will be retained for a longer period if required by the applicable regulatory requirements or by an agreement with the sponsor. It is the responsibility of the sponsor to inform the investigator/institution as to when these documents no longer need to be retained.

13.5.3 Data Management

Source documents will be developed, as needed, to capture necessary clinical data. The source documents are to be completed as soon as possible after the subject's visit, so that they reflect the latest observations for subjects participating in the trial.

All required clinical data will then be entered into the Clinical Trials Management System, OnCore. Electronic case report forms (eCRF) will be designed and developed to capture study specific data. All corrections or revisions to the eCRFs must be made by authorized personnel and an audit trail will be maintained.

All finalized data will be reviewed by the Investigator. Data recorded in the eCRFs will be retained by the site in accordance with FDA regulations.

13.5.4 Monitoring

Monitoring will be completed based on the Data and Safety Monitoring Plan in Appendix B.

13.5.5 Data Quality Assurance

Steps to be taken to assure the accuracy and reliability of data include the selection of qualified investigators, review of protocol procedures with the investigator and associated personnel prior to the study, and periodic monitoring visits by the sponsor. CRFs will be reviewed for accuracy and completeness by the CRO during on-site monitoring.

13.5.6 Use of Information and Publication

All information on SLM, patent application, manufacturing process and basic scientific data supplied by the sponsor to the investigator and not previously published is considered confidential and remains the sole property of the PI.

The investigator agrees to use this information only to accomplish this study and will not use it for other purposes without the sponsor's written consent.

The investigator understands that the information developed in the clinical study will be used by Sponsor in connection with the continued development of SLM and thus may be disclosed as required to other clinical investigators or government regulatory agencies.

To permit the information derived from the clinical studies to be used, the investigator is obligated to provide the sponsor with all data obtained in the study.

14.0 STATISTICAL CONSIDERATIONS

14.1 INTRODUCTION

This is a Phase I safety clinical trial with expansion cohort for assessing preliminary efficacy of the combination of axitinib and selenomethionine (SLM) for adult patients with advanced clear cell carcinoma (CCRCC). The Escalation Part 1 will determine the MTD of the combined treatment to be used for the proof of principle. The expansion cohort will be used to assess preliminary efficacy.

Summary statistics for continuous variables will include: mean, standard deviation, median and range. Categorical variables will be presented as frequency counts and percentages. Progression-free and overall survival will be summarized by Kaplan-Meier medians and survival plots. Data listings will be created to support tables and present data. The preliminary efficacy analysis will be conducted on the efficacy evaluable population and safety analysis will be performed on the safety population. SAS 9.3 or higher will be used for data analysis.

14.2 STUDY OBJECTIVES

The primary objectives of this study are:

- To characterize the safety profile of combining SLM and axitinib in advanced metastatic CCRCC and;
- To define the dose of SLM in combination with a standard dose of axitinib for phase 2 trial.

The secondary Objectives:

- To determine that the dose of SLM administered is sufficient to alter the expression levels of HIF1a, HIF2a, VEGF and their associated micro-RNAs 210, 155, and LET7b.
- To obtain preliminary estimates of efficacy in terms of:
 - Progression free survival (PFS),
 - Objective response rate (SD+PR+CR), and
 - Overall survival in patients with advanced metastatic CCRCC.

The exploratory objective is to define the PD effects of SLM.

14.3 ANALYSIS OF STUDY ENDPOINTS

14.3.1 Analysis of primary endpoint

a. The safety profile of the SLM and axitinib combination will be assessed by listing the overall incidence of AEs. The AEs will be summarized and classified by body system and by treatment group. The type, incidence, severity, and causality of each AE, the duration of the event, and any required treatment interventions will be tabulated. Physical examination results will be presented in the patient data listings. The DLT will be listed per dose level and treatment along with overall frequencies. The data from the expansion part will be used for this part of safety and tolerability assessment.

b. (Recommended Part 2 dose)

Dose level 1 (4000 µg) will be the starting dose in the standard 3+3 dose escalation design. Three patients will be recruited for Dose level 1.

The next three patients will be recruited for Dose level -1 (2500 µg). While none of the three patients in Dose level 1 experienced a DLT, there were significant side effects.

If 0 of three patients at Dose level -1 experiences a DLT related to SLM, then dose escalation will proceed to the next dose level (3000 µg).

If one of the three patients at Dose level -1 experiences a DLT related to SLM, then three more patients will be treated at the same dose. If exactly one out of six patients experiences a DLT, then dose escalation will proceed to the next dose (3000 µg) after discussion at the weekly SLM meeting.

If two of the first three patients experience DLT, then the dose will de-escalate to the lower dose (1500 µg).

The next patient can be enrolled after the previous patient's Day 28 assessment, provided there are no DLTs. The minimum number of patients required is 6 and the maximum is 12.

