2.3 CLINICAL STUDIES WITH SELENOMETHIONINE

Se compounds have been used in various clinical trials, mainly in chemo-prevention, at doses in the nutritional range (50 µg/day to 200 µg/day) without any toxicity (Casanovas). Since SLM was evaluated at higher doses 10 mg/kg/d in preclinical models where therapeutic synergy with anticancer drugs was demonstrated, clinical trials with escalating doses of SLM to achieve plasma concentration determined optimal in preclinical models were initiated at RPCI by [name], et al (Fakih) in combination with fixed dose of Irinotecan 125 mg/m² weekly. Different dose levels of SLM have been used (3200, 4000, 4800, 5600, and 7200 µg PO BID loading dose followed by once daily maintenance dose). A dose of 7200 µg/BID x 7 days followed by 7200 µg/QD for up to 36 days was determined sufficient and without toxicity. The only toxicity attributed to SLM was mild garlic-like odor (breath and urine) and was limited to G1 in about 50% of patients. This was seen more commonly during the induction SLM week and tended to ameliorate or disappear with prolonged treatment. No skin or nail toxicities secondary to SLM were documented.

Preliminary data from the initial trial indicate a single fixed dose of selenium conferred significant variability in patient blood selenium concentrations at the end of the 14-day run-in. Patient body surface area (BSA) was found to be a contributing factor with patients of lower BSAs more frequently having higher blood selenium concentration, although none of which were within the targeted range of 35-45 µM. Here we list the current subjects in 4 cohorts (C1: 4000 mcg, C2: 2500 mcg, C3: 3000 mcg and C4: 4000 mcg) and we list blood selenium concentration at D14, Cycle 2 and 7. There is clear difference in C 4 and C1 average blood concentration being higher in C 1 and associated with better responses.

Cohort	Pre	D14	C2	C7	Response
1	2.1	30.0	44.0	104.0	2CR, 1PR
2	2.0	14.0	21.0	25.0.	1PR, 1 PD
3	1.8	17.0.	25.0	43.0.	1PR, 2 PD
4	2.2	17.5	27	64	2 SD, 1 PD

CR (COMPLETE RESPONSE), PR (PARTIAL RESPONSE) SD (STABLE DISEASE) PD (PROGRESSIVE DISEASE)

IN LIGHT OF THESE FINDINGS, A MODIFIED DOSING SCHEME IS BEING INVESTIGATED WHICH VARIES THE DOSAGE OF SELENIUM BY BSA WITHIN A DOSE LEVEL TO ENSURE LESS VARIABILITY IN THE DOSE PER M2 ADMINISTERED.

2.4 HYPOXIA INDUCED FACTOR (HIF-A):

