5.6.1 CRITERIA FOR REMOVAL FROM STUDY

Patients will continue study treatment until any of the following occur:

- Disease progression (treatment beyond progression at the discretion of treating provider with confirmatory scan in 8 weeks if the patient is clinically doing well).
- Unacceptable toxicity
- Intercurrent illness that prevents further safe administration of treatment
- Withdrawal of consent
- Serious protocol violation
- Non-compliance to therapy regimen
- General or specific changes in the patient's condition rendering the patient unacceptable for further treatment, in the judgment of the investigator

The reason for study removal and the date the patient was removed must be documented on the Case Report Form.

5.7 END OF TREATMENT:

The end-of-treatment visit is to be conducted 28 days (+/- 7 days) after treatment discontinuation, and will include the following assessments:

- Physical examination
- Vital signs including blood pressure
- Assessment of ECOG performance status
- Clinical Chemistries
- CBC with differential
- Glucose
- Urinalysis
- Assessment of adverse events
- Concomitant medications
- Mandatory Fresh Tumor Tissue Biopsy at disease progression, for up to 20 patients in Expansion and pilot Phase, if accessible and deemed safe by physician.

5.8 EVALUABLE POPULATIONS:

For Escalation Part 1: the DLT evaluable population includes all patients who complete one cycle of SLM and patients who experience a DLT during the first cycle of dosing.

For Escalation Part 1 and Expansion Part 2: The safety population includes all patients who receive at least one dose of SLM.

For Expansion and Pilot Phase: The evaluable population includes all patients who have measurable disease at screening, according to RECIST criteria for the relapsed solid tumor cohort and undergo a baseline disease assessment and at least one on-treatment disease assessment. Evidence of disease progression including radiological assessments, hematological assessments, death due to disease progression, and study drug withdrawal due to disease progression will be counted as post-baseline disease assessments. Evaluation for clinical response will include only those with measurable disease at baseline and evaluation of progression will be evaluated in all patients regardless of measurable disease status at baseline.

6.0 SAFETY ASSESSMENTS:

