14.6 ANALYSIS POPULATIONS

The safety population will consist of all subjects receiving at least 1 dose of study medication. All subjects who received at least one dose of study treatment and had at least 1 post-baseline response evaluation will be included in the efficacy analysis set. Following completion of the study, best response will be determined for each subject in accordance with RECIST v.1.1 guidelines and the objective response rate presented for each dose cohort.

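### Section 14.3.1a names expansion-part data, and no other source, for the primary safety assessment, in conflict with its own by-dose DLT listing and with the all-treated safety population in 14.1, 14.6 and 12.2.1

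*Combined protocol and SAP*

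**What the plan says.** Section 14.3.1, item a, is the analysis text for the first primary objective, the safety profile of the combination (Sections 1.1 and 14.2). It calls for AEs to be tabulated by body system and treatment group, and then states: "The DLT will be listed per dose level and treatment along with overall frequencies". Its closing sentence is: "The data from the expansion part will be used for this part of safety and tolerability assessment".

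Three other places describe who is counted for safety:

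- Section 14.1: "safety analysis will be performed on the safety population".
- Section 14.6: "The safety population will consist of all subjects receiving at least 1 dose of study medication".
- Section 12.2.1: "All patients will be evaluable for toxicity from the time of their first treatment with SLM".

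Section 5.8 gives its own version: "For Escalation Part 1 and Expansion Part 2: The safety population includes all patients who receive at least one dose of SLM". The pilot is not mentioned there, although the next definition in 5.8 does name it: "For Expansion and Pilot Phase: The evaluable population includes all patients who have measurable disease at screening".

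**The concern.** The plan's only analysis text for primary objective 1 identifies one part of a three-part study as its data source. A programmer working from 14.3.1a alone could build the primary AE tables on the 19 expansion patients. Those tables would leave out the escalation patients, who supply the lower dose levels, and the pilot patients, who are the only ones who can be assigned more than 4000 mcg.

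The DLT listing would not make up for that. Pilot DLTs are counted only on Day 1 to 14 (Section 14.4), when SLM is given without axitinib (Section 5.3). Combination toxicity above 4000 mcg can therefore appear only in the AE tables, and the source of those tables is what is unclear.

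A second issue arises only on the opposite reading, when all parts are included. The request for overall DLT frequencies could then be met by adding escalation and pilot DLTs, which are defined over different windows and different event lists.

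**Working it through.** The plan states no figure on this point, so there is nothing to reproduce. The check compares the passages and counts the patients each one covers.

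**1. Can expansion data supply what 14.3.1a asks for?** Section 5.1 treats all 19 expansion patients at SLM 4000. A DLT listing by dose level drawn from that part would have one row. Section 5.8 defines a DLT-evaluable population only for Escalation Part 1. The listing therefore needs data from outside the expansion part, and the last two sentences of the item do not fit together.

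**2. Does the closing sentence agree with the safety population?** No. Section 14.1 sends the safety analysis to the safety population, and 14.6 defines that by receipt of one dose, with no restriction by part. Section 12.2.1 agrees. Because every patient starts with the SLM run-in (Section 5.3), counting from the first SLM dose (12.2.1) and from the first study medication (14.6) selects the same people.

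**3. How many patients would a literal reading omit?**

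- Escalation: 6 to 12 planned (Sections 5.1, 14.3.1b and 14.4).
- Expansion: 19 planned (Sections 5.1 and 14.4).
- Pilot: 10 planned (Schema).
- Planned total: 6 + 19 + 10 = 35, up to 12 + 19 + 10 = 41.
- Omitted = total − 19: 35 − 19 = 16, up to 41 − 19 = 22.
- Share omitted: 16/35 = 45.7%, up to 22/41 = 53.7%.

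**4. Which doses would be omitted?** The fixed levels in 5.1 are 1500, 2500, 3000 and 4000 mcg, and expansion uses 4000. The pilot table in 14.4 runs from 2000 to 8000 mcg. Its starting level assigns 4000, 5000 or 6000 mcg by BSA band. Every assignment above 4000 mcg is therefore in the pilot. The number of such patients cannot be given (0 to 10 of the planned 10), because no BSA distribution is stated.

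**5. Are the DLT definitions alike?** In escalation the window is the first cycle: 2 weeks of SLM alone plus 4 weeks of combination = 6 weeks, or 42 days. In the pilot it is 14 days of SLM alone. The ratio is 42/14 = 3, and only the longer window includes axitinib. The escalation list also counts study-drug-related treatment delays of more than 2 weeks, which the pilot list does not.

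**6. What does 5.8 cover as worded?** Escalation plus expansion, which is 6 + 19 = 25 to 12 + 19 = 31 patients.

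**The case against.** The best defence is that the plan already answers the question. Sections 14.1 and 14.6 state the rule, and 12.2.1 supports it. The closing sentence of 14.3.1a is not exclusive and could mean that expansion data also contribute: item b rests on escalation, and item a adds the expansion patients. Item a also asks for AEs by treatment group, which in a non-randomized study most naturally means dose or phase groups. Section 14.8 promises reports after Part 1. The output is descriptive, and neither AE recording (8.4) nor DSMC review (14.4) depends on it.

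Much of this stands. All-treated is the better reading, and a reader who inferred that the plan restricts primary safety to the expansion part would go further than the text. What remains is that the sentence names a single source in the very item that specifies the analysis. The Part 1 reports would not cover the pilot.

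Other stronger readings also fail:

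- **Both harms at once.** Omitting patients requires the expansion-only reading, and pooling unlike DLT windows requires the all-parts reading. Only one can occur. The plan also nowhere instructs that DLTs be pooled across phases; it asks for overall frequencies without saying over what.
- **Section 5.8 as a rule that excludes the pilot.** It does not say so, and 14.6 covers the pilot. That the line was missed in an amendment is an inference.
- **Escalation size taken from Section 2.3.** That section introduces its table with "Here we list the current subjects in 4 cohorts (C1: 4000 mcg, C2: 2500 mcg, C3: 3000 mcg and C4: 4000 mcg", and cohorts 1 to 3 show 3 + 2 + 3 = 8 responses. These are response entries and not patients dosed: cohort 2 shows two although 5.1 recruits three at that level, and cohort 4 is not assigned to a part. The planned range of 6 to 12 is the sound basis.

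**Conclusion.** The concern holds as a conflict within the text on the source of the primary safety analysis. The closing sentence of 14.3.1a is the one out of line, and it should be changed.

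If it is followed literally, 46% to 54% of planned patients are left out of the primary AE summary, along with every patient assigned more than 4000 mcg. If 14.1 and 14.6 are followed, nobody is left out. In that case the remaining risk is a DLT frequency that combines a 6-week window including axitinib with a 14-day window on SLM alone.

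The percentages rest on planned numbers, with escalation anywhere from 6 to 12. The pilot enrols cohorts of two evaluable patients, so the number dosed could exceed 10 and the omitted share could be higher. The documents give no figure for this, and none is assumed here. The omission of the pilot from the safety line in 5.8 is editorial. No test, sample size or dose decision is affected.

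**What to change.** Replace the last sentence of 14.3.1a with: *AEs are tabulated for the safety population defined in 14.6 (all patients in any part with at least one dose), overall and by phase and assigned dose level; DLTs are listed by phase under the definition and window that applies to that phase, and DLT frequencies are not pooled across phases with different definitions.*

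The request for overall DLT frequencies in the sentence before should be limited to match. The sponsor should also state which DLT definition, if any, applies to the expansion part. Section 5.1 limits only the treatment-delay item to the escalation phase, and 5.8 defines a DLT-evaluable set for escalation alone. As an editorial alignment, name the pilot in the 5.8 safety population.

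The AE tables would then follow the split by part and dose already planned for disposition (14.6.1) and baseline characteristics (14.6.2). The cost is a few sentences and some by-dose columns with small, purely descriptive counts. AEs are already recorded for every patient under 8.4, so no new data are needed, and AE collection and DSMC review do not change.
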